- a Randomization/baseline visit is defined as Day 1. The visit schedule should be adhered to within ±1 week for the 4-week screening period, ±3 days for the randomized IMP treatment period and ±5 days for the post IMP treatment period. If more than 12 weeks since last on-site scheduled visit, then unscheduled visit is required within 3 weeks of missed scheduled visit (eg, if missed scheduled visit at Week 24, then unscheduled visit must be performed by Week 27; If missed scheduled visit at Week 36, then unscheduled must be performed by Week 39). All the assessments of the missed scheduled on-site visit will need to be carried out at the unscheduled visit.
- b All assessments at Visit 2 (Day 1) are to be conducted pre-IMP dose with the exception of the assessment of local tolerability of SC injections.
- c End-of-treatment visit: See Section 7.1.1 for patients who discontinue treatment prematurely.
- d ECG to be centrally collected & read.
- Chest X-ray to be performed unless a <6-month-old chest x-ray/chest CT/chest MR is available. In case chest-X-ray is not feasible due to local regulations, magnetic resonance imaging (MRI) will be performed.
- f IMP (Dupilumab or placebo) is to be administered every 2 weeks by patient, caregiver or healthcare professional at the patient's home or in a health care facility. Last dose will be given at Week 50. If the patient or Investigator decides not to administer IMP at home, the IMP injections can be performed at the site by way of unscheduled visits. The IMP can be administered at home after training and at least 1 IMP injection at the site and supervised by the Investigator. Patients will be monitored at the study site for a minimum of 30 minutes after injections. See Section 6.1.1 for details. If the patient is unable or unwilling to administer IMP at home, injections can be performed at the site; or arrangements can be made for qualified site personnel and/or health care professionals (eg, visiting nurse service) to administer IMP for the doses that are not scheduled to be given at the study site.

Amended Clinical Trial Protocol 03 EFC15805 - dupilumab

28-Oct-2023 Version number: 1

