6.1.1 Investigational Medicinal Product(s)

The investigational medicinal product (IMP) is administered every 14 ± 3 days (q2w) during the 52-week treatment period (Table 2).

Investigational medicinal product (IMP) will be administered by the Investigator/health care professional or designee following clinic procedures and blood collection. Patients should be monitored for at least 30 minutes after administration of all IMP injections. The monitoring period may be extended as per country specific or local site-specific requirements.

Subcutaneous injection sites should alternate between the upper thighs, 4 quadrants of the abdomen or the upper arms, so that the same site is not injected twice during consecutive administrations.

The first IMP administration will be done by the Investigator or delegate. The patients are allowed to self-inject IMP at home after at least 1 injection at investigational site, supervised by the Investigator or delegate. To train patients how to prepare and inject IMP the Investigator will

28-Oct-2023 Version number: 1

first train the patient at the on-site visit during the treatment period. At this visit the patient will perform the injection under the supervision of the Investigator or delegate. This training must be documented in the patient's study file. Patient injection should only be performed in the abdomen or upper thighs. Patient should also be instructed to monitor for any reaction for at least 30 minutes (or longer per country specific or local site-specific requirements) following injection.

If the patient cannot take all the allocated IMP kits at home (eg. due to a storage issue), the DTP (Direct to Patient) service can be used or the patient may come to the site to pick-up the IMP kits. For doses not given at the study site, diaries will be provided to record information related to the injections. The diary will be kept as source data in the patient's study file.

If the patient is unable or unwilling to administer IMP at home, injections can be performed at the site; or arrangements can be made for qualified site personnel and/or health care professionals (eg, visiting nurse service) to administer IMP for the doses that are not scheduled to be given at the study site.

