9.2 SAMPLE SIZE DETERMINATION

The sample size of the study is determined based on power calculations for the primary endpoint of annualized rate of moderate or severe COPD exacerbations over the 52-week treatment period. Assuming the number of exacerbations following a negative binomial distribution with a dispersion parameter of 1, a placebo annualized rate of exacerbations being 1.5, an average treatment duration of 0.95 year (to account for an average of 5% of the planned treatment period with missing data), and a randomization ratio of 1:1 to the two treatment arms, with 924 randomized patients (462 for each treatment arm), the study will have 90% power to detect a 25% relative risk reduction (ie, annualized rate of 1.125 for the dupilumab group) in the annualized rate of moderate or severe COPD exacerbations at the 2-tailed significance level of $\alpha = 0.05$. With the addition of an interim analysis, the final alpha may be reduced to 0.049, which maintains approximately 90% power (see Section 9.5 for further details).

Patients will be randomized using a 1:1 randomization ratio to dupilumab 300 mg q2w or placebo. Randomization will be stratified by country, ICS dose (high dose ICS [yes/no]) at baseline, and

smoking status at screening (current smokers or not). As an example, the adult high dose of ICS for fluticasone propionate is >500 mcg (DPI or HFA) or 401-800 mcg (HFA) for Japanese population (please refer to Section 10.18 for the most common ICS). Alerts will be built into the IVRS/IWRS to limit enrolling patients who are current smokers (as defined by smoking status at screening) to less than or equal to 30% or 278 patients out of the total enrolled patients.

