2.3.2 Safety population

The safety population is defined as: All patients who actually received at least 1 dose or partial of a dose of the IMP, analyzed according to the treatment patients actually received.

In addition:

- Nonrandomized but treated patients will be part of the safety population
- Randomized patients for whom it is unclear whether they took the IMP will be included in the safety population as randomized
- For patients on placebo but accidentally exposed to dupilumab, the treatment group allocation for as-treated analysis will be dupilumab group
- For patients on dupilumab but accidentally receive placebo, the actual treatment group allocation for as-treated analysis will be dupilumab group

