2.4.5 Analyses of safety data

The summary of safety results will be presented by treatment group. All safety data collected up to the primary analysis cut-off date (either the IA cut-off date or cut-off date when last patient completes Week 52) will be included.

General common rules

All safety analyses will be performed on the safety population as defined in [Section 2.3.2](#), unless otherwise specified, using the following common rules:

- The baseline value is defined as the last available value before the first dose of IMP.
- The potentially clinically significant abnormality (PCSA) values are defined as abnormal values considered medically important by the Sponsor according to predefined criteria/thresholds based on literature review and defined by the Sponsor for clinical laboratory tests and vital signs and ECG [Appendix A]
- PCSA criteria will determine which patients had at least 1 PCSA during the treatment-emergent adverse event period, taking into account all evaluations performed during the treatment-emergent adverse event period, including nonscheduled or repeated evaluations. The number of all such patients will be the numerator for the on-treatment PCSA percentage

- The treatment-emergent PCSA denominator by group for a given parameter will be based on the number of patients assessed for that given parameter in the treatment-emergent adverse event period by treatment group on the safety population.
- For quantitative safety parameters based on central laboratory/reading measurements, descriptive statistics will be used to summarize results and change from baseline values by visit and treatment group. Summaries will include the endpoint value and/or the worst on-treatment value. The endpoint value is commonly defined as the value collected at the end of treatment. If this value is missing, this endpoint value will be the closest value prior to the end of treatment epoch. The worst value is defined as the nadir and /or the peak post-baseline (up to the end of treatment epoch or EOT) according to the direction (minimum or maximum) of the abnormality as defined in the PCSA list
- The analysis of the safety variables will be essentially descriptive and no systematic testing is planned. Relative risks versus placebo and their 95% confidence intervals may be provided, if relevant
- All safety values including unscheduled measurements will be assigned to the appropriate safety analysis visit window defined in [Section 2.5.3](#).

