2.4.5.1 Analyses of adverse events

Generalities

The primary focus of adverse event reporting will be on treatment-emergent adverse events. Pretreatment and posttreatment adverse events will be described separately.

If an adverse event date/time of onset (occurrence, worsening, or becoming serious) is incomplete, an imputation algorithm will be used to classify the adverse event as pretreatment, treatment-emergent, or posttreatment. The algorithm for imputing date/time of onset will be conservative and will classify an adverse event as treatment emergent unless there is definitive information to determine it is pretreatment or posttreatment. Details on classification of adverse events with missing or partial onset dates are provided in [Section 2.5.2](#).

Adverse event incidence tables will present by SOC, HLT, HLT, and PT, sorted in alphabetical order for each treatment group, the number (n) and percentage (%) of patients experiencing an adverse event. Multiple occurrences of the same event in the same patient will be counted only once in the tables within a treatment phase. The denominator for computation of percentages is the safety population within each treatment group.

Sorting within tables ensures the same presentation for the set of all adverse events within the observation period (pretreatment, treatment-emergent, and posttreatment). For that purpose, the table of all treatment-emergent adverse events presented by SOC and PT sorted by the internationally agreed SOC order and decreasing frequency of PTs within SOCs will define the presentation order for all other tables unless otherwise specified. Sorting will be based on results for the dupilumab 300 mg q2w group.

Risk differences (constructed using the Miettinen and Nurminen method) and hazard ratios (Cox proportional hazards model) for dupilumab versus placebo with corresponding 95% CIs will be provided for the overview table, common TEAEs (PT $\geq 1\%$, 2%, 5% in any intervention

group), and AESIs and other selected AE grouping events table. Participants without an event will be censored at the end of the treatment-emergent period in the Cox model. Forest plots will also be presented.

Analysis of all treatment-emergent adverse events

The following treatment-emergent adverse event summaries will be generated for the safety population.

- Overview of treatment-emergent adverse events, summarizing number (%) of patients with any:
 - Treatment-emergent adverse event

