 - Number (%) of patients with any specific TEAE
 - Number (%) of patients with any specific serious AE (regardless of treatment emergent status)
 - Number (%) of patients with any specific treatment emergent serious AE
 - Number (%) of patients with any specific AE leading to death
 - Number (%) of patients with any specific TEAE leading to permanent study drug discontinuation

- Number (%) of patients with any specific TEAE related to IMP reported by investigator
- Number (%) of patients with any specific TEAE by maximum intensity, corrective treatment, and final outcome
- Number of any specific TEAE adjusted by the exposure duration
- Number of patients with any specific TEAE adjusted by the exposure duration at risk. For each specific TEAE, Kaplan-Meier estimates of cumulative incidence at Week 12, 24, 36 and 52 and K-M plot may be provided to depict the course of onset over time if the number of events is large enough.
- Number (%) of patients with injection site reactions by the related injection.
- Number (%) of patients with different number of injection site reactions.
- In addition, AESIs reported by the investigator in CRF will be summarized separately.

Analysis of pretreatment adverse events

- All pretreatment adverse events by primary SOC and PT, showing the number (%) of patients with at least 1 pretreatment adverse event, sorted by the internationally agreed SOC order and decreasing incidence of PTs within each SOC in the 300 q2w treatment group.
- All serious pretreatment adverse events by primary SOC and PT, showing the number (%) of patients with at least 1 pretreatment adverse event, sorted by the internationally agreed SOC order and decreasing incidence of PTs within each SOC.
- All pretreatment adverse events leading to permanent treatment discontinuation by primary SOC and PT, showing the number (%) of patients, sorted by the internationally agreed SOC order and decreasing incidence of PTs within each SOC.
- All pretreatment adverse events leading to death by primary SOC and PT, showing the number (%) of patients, sorted by the internationally agreed SOC order and decreasing incidence of PTs within each SOC.
- If only a few patients have pretreatment adverse events leading to permanent treatment discontinuation, a listing will be presented instead of the summary table above.

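### Injection site reactions by injection: the whole-safety-population base understates percentages at later injections, and the once-per-phase counting rule does not fit the table

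*SAP*

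**What the plan says.** In its list for adverse events of special interest and other selected groupings, SAP 2.4.5.1 plans "Number (%) of patients with injection site reactions by the related injection". That line sets no denominator, does not define the related injection, and does not say how a patient with several reactions is counted.

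Two general rules stand earlier in the same section, under Generalities:
- "The denominator for computation of percentages is the safety population within each treatment group"
- "Multiple occurrences of the same event in the same patient will be counted only once in the tables within a treatment phase"

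SAP 2.3.2 defines the safety population as "All patients who actually received at least 1 dose or partial of a dose of the IMP". It is fixed over time, so it matches the number exposed at injection 1 only.

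Dosing is every two weeks from Week 0. The schedule of activities (Protocol 1.3.1) states "Last dose will be given at Week 50", which makes 26 planned injections.

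On timing, SAP 2.4.5 includes "All safety data collected up to the primary analysis cut-off date (either the IA cut-off date or cut-off date when last patient completes Week 52". SAP 4 makes the interim lock the primary analysis for all endpoints if the interim demonstrates efficacy.

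**The concern.** A by-injection table invites the reader to look along the row and ask whether reactions become more or less frequent with repeated dosing. On a fixed base, three kinds of patient count as reaction-free at injection k although they never received it: those who stopped earlier, those who skipped that dose, and those not yet due for it at the cut-off. All three pull the later percentages down.

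The counting rule adds a second problem. Applied to this table, it would place a patient with repeated reactions under one injection only, and the SAP does not say which one.

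At stake is the time pattern of local tolerability. Part of an apparent waning could come from the choice of base.

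**Working it through.** The plan states no figure for this table. The one design input used is the mean duration in Protocol 9.2, "an average treatment duration of 0.95 year (to account for an average of 5% of the planned treatment period with missing data".

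**The plan's own figure.** With 462 per arm, rates 1.5 and 1.125, dispersion 1 and duration 0.95:
- SE of the log rate ratio = √{[(1/(1.5×0.95)+1) + (1/(1.125×0.95)+1)]/462} = 0.0887.
- Power = Φ(|ln 0.75|/0.0887 − 1.96) = 90.0%, as stated. At α = 0.049 it is 89.9%.

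This confirms the design inputs, including the 0.95. The point itself does not depend on power.

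**Model for the table.** Let p be a constant true risk per injection actually given, and R(k) the share of the safety population that received injection k. The table then shows p × R(k). With patients who received injection k as the base, it shows p at every k.

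**Week 52 lock.** Assume a constant discontinuation hazard λ per year with (1 − e^−λ)/λ equal to the mean duration. Injection 13 falls at Week 24 and injection 26 at Week 50, so R = e^(−λ·24/52) and e^(−λ·50/52).

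| Mean duration (years) | R(13) | R(26) | Relative understatement at injection 26 |
|---|---|---|---|
| 0.97 | 0.972 | 0.943 | 6% |
| 0.95 | 0.953 | 0.905 | 10% |
| 0.92 | 0.925 | 0.850 | 15% |
| 0.90 | 0.906 | 0.814 | 19% |

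**Interim cut-off as primary analysis.** Let f be the information fraction. Assume the remaining follow-up of ongoing patients is uniform on 0 to W weeks. W cannot exceed about 40, because SAP 3 says all participants will have complete Week 12 follow-up.
- Ongoing share: q = (1 − f)/(W/2/52).
- Share past Week 50: 1 − q(1 − 2/W), multiplied by 0.905 for discontinuation at mean duration 0.95.
- Example, f = 0.92 and W = 40: q = 0.08/(20/52) = 0.208. The share past Week 50 is 1 − 0.208×0.95 = 0.802, and 0.802×0.905 = 0.726.

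| f | W (weeks) | q | R(26) | Relative understatement |
|---|---|---|---|---|
| 0.92 | 40 | 0.208 | 0.726 | 27% |
| 0.92 | 26 | 0.320 | 0.638 | 36% |
| 0.92 | 16 | 0.520 | 0.493 | 51% |
| 0.96 | 40 | 0.104 | 0.816 | 18% |
| 0.96 | 26 | 0.160 | 0.772 | 23% |
| 0.96 | 16 | 0.260 | 0.699 | 30% |

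The loss is concentrated late. At injection 13 with f = 0.92, the cut-off alone removes about 6% for W = 40 (0.208 × (1 − 28/40) = 0.062) and nothing for W = 26 or 16.

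**Illustration.** With an assumed p of 3%, injection 26 would show about 2.7% at a Week 52 lock (3% × 0.905). At an interim cut-off at 0.92 it would show 1.5% to 2.2% (3% × 0.493 to 3% × 0.726).

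**The case against.** **The denominator is inferred.** The general rule sits in a paragraph about incidence tables by system organ class and preferred term. Its companion counting rule makes little sense for a by-injection table, so the paragraph may not have been written with this table in mind. That is fair: the line leaves its base unstated rather than specifying a wrong one. But the SAP gives no other rule for adverse event percentages, so a programmer following the text would use the safety population.

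**Other outputs cover exposure.** Injection site reactions are a selected grouping in SAP Table 2, so they also get exposure-adjusted summaries, Cox hazard ratios and optional Kaplan-Meier estimates. SAP 2.4.3.1 tabulates duration of exposure by category. These make a false reading easier to avoid, but none gives a risk per injection.

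**The large figures need a successful interim.** This stands. They also apply to the last injection only. SAP 4 plans a further lock once all patients have completed or left, so late-injection data do accrue.

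**The table is descriptive.** This stands. With similar exposure both arms are deflated by the same factor, and the ratio between them is unchanged.

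**Home dosing.** A reader might infer that reactions also go unrecorded later because dosing moves home. Only 8 of 26 scheduled doses fall on on-site visits (Weeks 0, 2, 4, 8, 12, 24, 36 and 44): 6 of the first 13 and 2 of the last 13. The documents do not support that inference. Protocol 6.1.1 says "The patients are allowed to self-inject IMP at home after at least 1 injection at investigational site", which is permission and not a requirement. Dosing at the site or by a health professional remains available. Adverse events are collected at every visit, telephone visits included, and patients are told to monitor themselves after home injections. No figure for lower reporting at home is given.

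**Conclusion.** The point holds as a minor one. Under the SAP's general rule, percentages by injection are biased downward at later injections. With a constant true risk, the relative understatement at injection 26 is about 10% at a Week 52 lock (6% to 19% over the range of mean durations tried), and about 18% to 51% if an interim cut-off at information fraction 0.92 to 0.96 becomes the primary analysis.

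The sizes rest on a constant discontinuation hazard, uniform remaining follow-up among ongoing patients, and independence of the two; the documents give none of these. The 5% in Protocol 9.2 describes missing follow-up. Patients may stop drug, or skip doses, and stay in the study, so the share receiving late injections could be lower than computed.

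A reader might infer that the displayed rate must fall with time on drug. That is too strong: the percentage is deflated by the share dosed, but it falls only if the true risk per injection does not rise enough to offset this. Nor does either document claim that reactions wane.

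**What to change.** In SAP 2.4.5.1, state for this table that:
- the related injection means injection number;
- the denominator for injection k is the patients in each arm who received injection k by the cut-off date;
- each patient is counted once per injection, in place of once per treatment phase;
- the denominator is shown for every injection.

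The SAP already follows this principle for potentially clinically significant abnormalities in 2.4.5, where the base is the patients assessed for the parameter. Compliance in 2.4.3.2 is already defined administration by administration, so records at injection level are needed anyway.

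The cost is a short addition to the text and a changed table shell, with no effect on trial conduct, blinding or alpha. The downside is smaller denominators, and so less precision, at late injections.

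A split into site and home doses is not needed. Off-site doses may be given by a professional, so the split would not separate supervised from unsupervised dosing, and the documents do not say that dosing location reaches the analysis database.

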2.4.5.2 Deaths

The following summaries of deaths will be generated for the safety population.

- Number (%) of patients who died by study period (TEAE, on-study, on-treatment, poststudy).
- Deaths in nonrandomized patients or randomized but not treated patients.
- Treatment-emergent adverse events leading to death (death as an outcome on the adverse event case report form page as reported by the Investigator) by primary SOC, HLT, HLT, and PT showing number (%) of patients sorted by internationally agreed SOC order, with HLT, HLT, and PT presented in alphabetical order within each SOC.
- All pretreatment adverse events leading to death by primary SOC and PT, showing the number (%) of patients, sorted by the internationally agreed SOC order and decreasing incidence of PTs within each SOC.

A listing of deaths will be provided.

